8.4.4. Reporting Procedure to Ethics Committee (EC) and to Regulatory Authorities

In addition to informing the Study Safety Contact, the Investigator shall notify SAE to his/her EC as applicable (in particular in case of death); in addition, for reported deaths of a subject, the Investigator shall supply Study Safety Contact and the Ethics Committee with any additional information requested. Copies of all correspondence relating to reporting of any SAEs to the EC should be maintained in the Investigator's Files.

Dompé Pharmacovigilance shall submit any suspected unexpected serious adverse reaction (SUSAR) to the concerned EC and Regulatory Authority (via Eudravigilance), as soon as possible and in no event later than:

- seven calendar days after becoming aware of the information if the event is fatal or life threatening; to be followed by any relevant information within eight days.

- fifteen calendar days after becoming aware of the information if the serious event is neither fatal nor life threatening.

Dompé Pharmacovigilance shall report any relevant updated follow-up safety information as soon as available.

If the results of an investigation show that an ADR not initially determined to be reportable is reclassified as reportable, Dompé Pharmacovigilance shall report such reaction in a written safety report as soon as possible, within the timeframes defined by current law requirements.

Dompé shall be responsible to prepare and submit annual safety reports (Development Safety Update Report – DSUR) to relevant Regulatory Authorities, as applicable. In addition, Investigator will receive from Dompé Pharmacovigilance appropriate periodic safety updates, as per applicable local requirements and regulations.

Dompé will ensure ongoing safety evaluation to be conducted periodically during the study on the safety data received, including monitoring of AESI.

8.5. EXPOSURE TO INVESTIGATIONAL PRODUCT DURING PREGNANCY

Women of childbearing potential are not excluded from the study as long as adequate birth control methods are being utilized. Women of childbearing potential are defined as all women physiologically capable of becoming pregnant. Prior to enrolment in the clinical trial, female patients of childbearing potential and their partners must be advised of the importance of avoiding pregnancy during the entire course of the study treatment and for the 30 days after the study treatment period ends and of the potential risks associated with an unintentional pregnancy. During the trial, female patients are to be instructed to contact the Investigator immediately if they suspect they might be pregnant. In the same way, male patients who become aware that the partner might be pregnant, are to be instructed to contact the Investigator immediately.

The Investigator must report every pregnancy on a Pregnancy Report Form as soon as possible (within 24 hours of learning of the pregnancy to the Study Safety Contact (contacts specified in the section “Contact Information”), even if no AE has occurred, and follow it up to term. If, however, the pregnancy is associated with an SAE (e.g., if the mother is hospitalized for dehydration), in addition to the Pregnancy Report Form, a separate SAE Report Form must be filed as described in Section 8.4.1 with the appropriate serious criterion (e.g., hospitalization) indicated on the SAE Report Form. Miscarriage, stillbirth and any malformation/disease must be reported as a SAE.

Any pregnancy leads to the immediate exclusion from the trial.

8.6. ADVERSE EVENTS CAUSING TREATMENT DISCONTINUATION

If a patient is withdrawn from the study as a consequence of an AE, this must be recorded in the eCRF, and the patient must be followed up until the resolution of the AE or as instructed by the medical monitor.

8.7. OVERDOSE

Cases of overdose (accidental or intentional) which may or may not result in serious adverse reactions are to be reported to Study Safety Contact, following the same procedure for SAE, within 24 hours from

the Investigator's knowledge of its occurrence. The Medical Expert should be contacted to discuss corrective treatment, if necessary.

An overdose of the study drug is defined as:

- Capsules: The administration of more than 50% of the daily dose

Overdose includes reports related to drug intake through different routes (e.g. ingestion) or with suicidal intentions and consequent drug overdose.

The Investigator shall provide in the SAE form information about symptoms, corrective treatment and outcome of overdose.

8.8. UNBLINDING

During the trial, blinding may be broken by the Investigator for emergency purposes only, when knowledge of the treatment identity is essential for treating the subject, or by Sponsor Pharmacovigilance for safety reasons and in case of Serious Adverse Events qualifying for regulatory reporting (SUSAR), in line with regulatory requirements.

If the treatment code needs to be broken in the interest of patient's safety for a medical emergency, the Investigator is allowed to break the treatment code for the specific patient, even before informing the Sponsor. Investigator will be allowed to unblind study medication electronically through a specific procedure within the eCRF (GENIUS IWRS). The system will notify the unmasking via e-mail to the Study Safety Contact and Dompé Medical Expert without revealing the treatment identity, but only referring to the kit number involved in the unmasking in order to avoid a dissemination of unmasked information. Proper training as well a specific user's manual is provided to investigators for the use of GENIUS IWRS and of the unblinding functionality. As a backup solution, sealed envelopes containing the individual treatment codes will be available at sites and must be kept by the Investigator in a secure location accessible only to designated staff in order to avoid dissemination of treatment identification to personnel involved in study conduct who must remain blind. During the study, the integrity of the envelopes will be regularly checked by the Site Monitor, during the visits at site. At the end of the study, all the individual envelopes must be returned to Dompé.

Dompé Drug Safety may need to unmask a patient's treatment for safety reason or if a reported SAE meets criteria of a SUSAR in order to fulfil expedited regulatory reporting requirements. Dompé Drug Safety will be allowed to unblind study medication electronically through the specific procedure within the eCRF (GENIUS IWRS). Additionally, a copy of the individual envelopes identified with the subject assignment number/ kit number will be also provided to the Dompé Drug Safety before study start, together with access to the GENIUS IWRS. The identity of the treatments will remain unknown to the subject, Investigator, site staff, CRO and Dompé Development personnel until the study completion and formal unmasking.

The randomization code will be broken when the last enrolled patient has completed therapy, and once the database has been locked.

9. STATISTICS

9.1. SAMPLE SIZE

The sample size of the study is calculated based on the following assumptions:

- Virologic assumption: Early treatment with antivirals increases the proportion of patients with undetectable SARS-CoV-2 in upper respiratory tract at day 7 after therapy from 25% to 50%;
- Clinical assumption: Early treatment with antivirals increases the proportion of participants who recover without need of mechanical ventilation and/or supplemental oxygen therapy by the day 14 after therapy from 50% to 75%.

Based on these assumptions and considering a randomization ratio 1:1:1, the sample size will be adaptively determined to achieve a power greater than 80% to show superiority of raloxifene vs placebo in terms of either one primary endpoint (section 7.1.1) and controlling the one-sided alpha below 0.025.

Sample size will be determined through the following steps:

- an interim analysis will take place when 50 participants per arm (N=150) have reached their primary endpoints (i.e. assessments available).
 - In case of efficacy of at least one treatment arm or futility of both arms (see criteria in section 9.3) the study enrolment will be stopped,
 - otherwise the actual number of new participants in each arm may be blindly reassessed according to observed efficacy of the best favourable and promising arm;
- in case of continuation of the study to the final stage, it is expected to randomize on average additional 174 patients, depending on sample size reassessment and possible dropping of an ineffective treatment arm. Expected sample size will be between 250 and 450 randomized participants;
- drop-outs of randomized subjects will not be replaced.

This approach allows either to minimize the number of enrolled participants if the experimental assumptions are too conservative or to have a good power level if they are too optimistic.

Pocock's spending functions and conditional power (CP) will be used to control the type I and II errors, considering that interim analysis will be performed when half of the initial planned patients have been reached the primary endpoints (i.e. assessments available).

Bonferroni method is used to adjust for multiple endpoint vs treatment comparisons.

Sample size calculation has been performed through simulation (100000 replications). The statistical software used for simulation was SAS®, Version 9.4.

9.2. RANDOMIZATION

Eligible Patient will be randomized in a 1:1:1 fashion to either:

- Group 1: 1 capsule of raloxifene 60 mg and 1 capsule of placebo.
- Group 2: 2 capsules of raloxifene 60 mg.

- Group 3: 2 capsules of placebo.

Randomization will be performed through IRS. Each Patient Kit number will be randomly associated with a treatment group. The randomization list will be provided to the facility responsible for IMP packaging/labelling for the purpose of IMP preparation. Each randomized patient will be allocated with randomization number according to the stratified randomization list. Dropouts after randomization will not be replaced.

Randomization will be stratified by site and gender to ensure balanced assignment across treatment groups. The stratified permuted block randomization list will be generated with a computer procedure by an independent statistician not involved in the conduct of the study.

Access to individual patient treatment code will be allowed only in the event of a medical emergency where the knowledge of patient treatment is required to provide the patient with appropriate care. The investigator will be provided with a protected access to the randomization system to allow opening of the treatment allocation for a specific patient in case of a medical emergency.

Dompé Pharmacovigilance contact person will be provided with a protected access to the randomization information in case of unblinding for safety procedures.

Unblinding events will be recorded and reported in the final study report.

The randomization codes will be accessible to the independent statistician who will perform the interim analysis. The treatment assignment information will be kept confidential and will not be disclosed to any other person than those ones involved in these intermediate analysis.

The randomization code will be broken according to study procedures after the last enrolled patient has completed his/her follow-up visit.

9.3. STATISTICAL METHODOLOGY

An interim analysis is planned when half of the planned evaluable patients has reached the primary endpoints at 7 and 14 days (i.e. assessments available). The intent of the interim analysis is either for identification of early superiority of raloxifene (early efficacy), or for an early stop of one or both treatment arms for futility, or for blind sample size reassessment.

Pocock's spending functions and CP will be used to control the type I and II errors for analyses of primary endpoints. Pocock's boundaries (on standardized Z scale) for efficacy and futility at interim and final analyses are reported in Table 1.

Table 1: Pocock spending functions boundaries for primary endpoints

Analysis	Sample Size	Standardized Z Scaleboundaries for primary endpoints	
		Alpha	Beta
Interim	50%	2.69640	1.59184
Final	100%	2.69640	2.69640

The analysis will be conducted by an independent statistician who will communicate to the Sponsor the result of the interim analysis and the consequent decisions on the continuation of the study, drop of an unefficacious treatment arm and on the reassessment of sample size, if required.

On the basis of Pocock's boundaries and CP at interim analysis, each treatment arm will be classified and ranked as "Effective", "Favorable", "Promising", or "Unfavorable". According to the most effective up-ranked arm, a decisions on the continuation of the study and on the reassessment of sample size will taken.

In case only one treatment arm is defined as "Unfavorable" at the interim analysis, this arm will be dropped from the continuation of study and no additional subjects will allocated to it. Already randomized subjects will continue the follow-up as planned.

Criteria for classification and ranking of treatment arms and possible consequent actions are reported in Table 2.

Table 2: Criteria for classification of treatment arms and actions post-interim analysis

Arm Classification	Criteria		Action based on the most up-ranked treatment arm
	Pocock's Alpha	Higher Conditional Power between Virologic and Clinical endpoint	
1 - Effective	Z > 2.69640	AND CP>90%	Stop for efficacy
2 - Favorable	-	CP>80%	No sample size reassessment
3 - Promising	-	35%<CP≤80%	Sample size reassessment
4 - Unfavorable	Z ≤ 1.59184	OR CP≤35%	Stop for futility

9.4. PATIENT POPULATION

The following population will be defined:

- The Safety (SAF) population will consist of all randomized patients who received at least one dose of the investigational product. Safety population will be analyzed according to the actual treatment received. The SAF population will be used to present results on safety data.
- The Full Analysis Set (FAS) population will consist of all randomized patients who received at least one dose of the investigational product. FAS population will be analyzed according to ITT principle, i.e. by treatment allocation regardless happening of intercurrent events. The FAS population will be used for the primary analyses of the study and to present results on efficacy data.

The Per Protocol (PP) population will consist of all randomized patients who received at least one dose of the investigational product and do not have Major Protocol Deviations. The PP population will be used for sensitivity analyses.

9.5. STATISTICAL METHODOLOGY

All patient data collected on the eCRF will be listed by patient and center.

Appropriate descriptive statistics will be produced, according to the variable:

- for continuous data n, mean, standard deviation (SD), median and range (minimum and maximum) will be presented;
- for categorical data, frequency distributions and percentages will be presented;
- for time-to-event variables, cumulative freedom from event will be evaluated using Kaplan-Meier method. The degree of uncertainty will be expressed with 95% confidence limits (calculated per the method proposed by Greenwood). Comparison of curves among arms will be performed with the log-rank test. Kaplan-Meier graphs will be presented along with the number of patient-at-risk at exact time points. Subjects ongoing and who are free from event at the time of DB lock will be censored at the DB lock date. Subjects who have discontinued without an event will be censored at the date of discontinuation.

Unless otherwise specified, the significance level used for statistical testing will be 0.05 and two-sided tests will be used.

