9.5.2.2. Secondary analyses

All secondary endpoints will be analyzed at each available timepoints by means of descriptive statistics and by appropriate parametric tests depending on the nature of the variable and its distribution. Data transformation might be used in order to satisfy the assumption of normality requested by parametric statistical tests. In case such assumptions are not met, non-parametric counterpart tests will be used. Change from baseline value (for continuous variables) and shift tables versus baseline (for categorical variables) will also be summarized for all post-baseline visits.

The incidence of participants with undetectable SARS-CoV-2 at PCR, the incidence of participants who requires supplemental oxygen therapy (NEWS ≤ 2) and/or mechanical ventilation, and mortality will be analyzed as proportion at each time point and as time-to-event.

Details will be provided in the SAP.

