3.2.2 SECONDARY ENDPOINTS

- Proportion of patients with undetectable SARS-CoV-2 at PCR at day 14 after randomization at day 28 after randomization.
- Proportion of patients who does not require supplemental oxygen therapy

(NEWS ≤2) and/or mechanical ventilation at day 7 and 28 after randomization.

- Proportion of patients in each NEWS category at time 7, 14 and 28 after randomization.
- Mean value of NEWS category at time 7, 14 and 28 after randomization.
- Proportion of patients with any adverse event with grade ≤ 2 according to CTCAE at day 7, 14 and 28 after randomization.
- Proportion of patients with any severe adverse events (grade ≥ 3 according to CTCAE) at day 7, 14 and 28 after randomization.
- Proportion of hospitalized patients who at the beginning of the study were at domicile isolation at day 7, 14 and 28 after randomization.
- Proportion of patients admitted to intensive care at day 7, 14 and 28 after randomization.
- Proportion of survivors at day 7, 14 and 28 after randomization.
- Mean variation of value of the following biomarker parameters, from baseline to day 7, 14, 21 and 28 after randomization:
 - Complete blood cell counts.
 - Hepatic function (ALT, AST and bilirubin).
 - Coagulation (PT, aPTT and INR).
 - Other marker including (D-dimer, CPK, LDH).
- Quality of life questionnaire 3 months after the randomization.

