4.1.2 SAMPLE SIZE

The sample size of the study has been based on the following assumptions:

- Virologic assumption: Early treatment with antivirals increases the proportion of patients with undetectable SARS-CoV-2 in upper respiratory tract at day 7 after therapy from 25% to 50%.
- Clinical assumption: Early treatment with antivirals increases the proportion of

patients who recover without need of mechanical ventilation and/or supplemental oxygen therapy by the day 14 after therapy from 50% to 75%.

Based on these assumptions and considering a randomization ratio 1:1:1, the sample size will be adaptively determined to achieve a power greater than 80% to show superiority of raloxifene vs placebo in terms of either one of primary endpoint and controlling the one-sided alpha below 0.025.

Sample size will be determined through the following steps:

- an interim analysis will take place when 50 patients per arm (N=150) have reached their primary endpoints (i.e. assessments available).
 - In case of efficacy of at least one treatment arm or futility of both arms (see criteria in protocol section 9.3) the study enrollment will be stopped,
 - otherwise the actual number of new patients in each arm may be blindly reassessed according to observed efficacy of the best favourable and promising arm;
- in case of continuation of the study to the final stage, it is expected to randomize on average additional 174 patients, depending on sample size reassessment and possible dropping of an ineffective treatment arm. Expected sample size will be between 250 and 450 randomized patients;
- drop-outs of randomized subjects will not be replaced.

This approach allows either to minimize the number of enrolled patients if the experimental assumptions are too conservative or to have a good power level if they are too optimistic.

Pocock's spending functions and conditional power (CP) will be used to control the type I and II errors, considering that interim analysis will be performed when half of the initial planned patients have been reached the primary endpoints (i.e. assessments available).

Bonferroni method is used to adjust for multiple endpoint vs treatment comparisons. Sample size calculation has been performed through simulation (100000 replications). The statistical software used for simulation was SAS®, Version 9.4.

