4.3 INTERIM ANALYSIS

An interim analysis was planned for this study when half (i.e 50 participants per arm (N=150)) of the planned evaluable patients would have reached the primary endpoints at 7 and 14 days (i.e., assessments available).

The intent of the interim analysis was either for identification of early superiority of raloxifene (early efficacy), or for an early stop of one or both treatment arms for futility, or for blind sample size reassessment.

Due to the premature interruption of the enrolment (with 68 patients included in the study), no interim analysis will be done.

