4.4 OVERALL ANALYSIS

Final analyses identified in this SAP will be performed by Agati Clinical Informatics following Sponsor Authorization of this Statistical Analysis Plan, Database Lock, Sponsor Authorization of Analysis Population and Unblinding of Study Treatment.

For primary and secondary efficacy endpoints, p-value, lower and upper 95% Confidence Limits (CL) will be also presented based on the statistical analysis performed.

The default summary statistics for quantitative variables will be the number of observations (n), mean, standard deviation (SD), median, minimum (min) and maximum (max).

For qualitative variables, the number (n) and percentage (%) of patients with non-missing data per variable of interest will be the default summary presentation, if appropriate and wherever required the number of missing values will be presented as a "Missing" category. If appropriate, 95% confidence intervals around the percentage will be presented.

Time-to-event endpoints will be assessed by the Kaplan-Meier (K-M) method. Time to event curves will be compared (i.e comparisons of each active treatment group versus placebo) using log-rank test and estimates of hazard ratio will be obtained using Cox proportional hazards model after performing diagnostics of proportional hazard assumption (investigated with a time dependent exploratory variable treatment*{log[time to event]}); if the p-value from the Wald Chi-squared statistic for this variable is less than 5% there is evidence of a departure from the adjusted model assumptions.). K-M estimates of median survival time associated with each treatment group will be provided along with 25th and 75th percentiles and their 2-sided 95% CIs (based on Greenwood's method). K-M estimates will be presented at Day 7, 14 and 28 for each treatment group. K-M curves will be plotted comparing treatment groups with the number of patient-at-risk in each treatment group at exact time points. Patients who are ongoing and who are free from event at the time of DB lock will be censored at the DB lock date. Patients who have discontinued without an event will be censored at the date of discontinuation. Patients who are died will be considered as censored with death

date as date of censored.

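### Greenwood limits give no usable interval for survival in an arm without deaths, a likely outcome at about 23 patients per arm if mortality is low

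*Protocol*

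**What the plan says.** Protocol 9.5 sets the general rule for time-to-event variables, Kaplan-Meier curves with Greenwood limits: "The degree of uncertainty will be expressed with 95% confidence limits (calculated per the method proposed by Greenwood". It does not name the scale on which the limits are formed (linear, log or log-log).

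SAP 4.4 repeats Greenwood for the median and quartiles, with "their 2-sided 95% CIs (based on Greenwood's method". It then adds landmark estimates, "K-M estimates will be presented at Day 7, 14 and 28 for each treatment group", without naming an interval for them. SAP 14.1.2 sends overall survival to the methods of 4.4.

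Survival is a listed secondary endpoint in SAP 3.2.2: "Proportion of survivors at day 7, 14 and 28 after randomization". Protocol 9.5.2.2 promises that "mortality will be analyzed as proportion at each time point and as time-to-event", but SAP 14.1.2 gives survival only a time-to-event analysis.

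The SAP was written knowing the reduced size: "Due to the premature interruption of the enrolment (with 68 patients included in the study), no interim analysis will be done". For statistics that cannot be computed, SAP Appendix 1 prints NE with a footnote saying there are too few data. Neither document says what interval to give an arm with no deaths.

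**The concern.** Greenwood's formula builds the variance from the observed events. With no events it returns zero, so the method cannot express uncertainty where a reader of a small trial most needs it. Patients enter with NEWS of 2 or less and no need for oxygen, so an arm with no deaths is plausible.

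If the table prints 100%-100%, it says that survival is known exactly. If it prints NE, it gives no bound, although one is easily computed. The SAP provides no other interval for survival that is sure to appear: 4.4 allows confidence intervals around percentages only where appropriate and names no method.

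**Working it through.** **Inputs.** Total 68 (SAP 4.3). Allocation is equal (SAP 4.1.2: "considering a randomization ratio 1:1:1, the sample size will be adaptively determined"). So 68/3 = 22.7, about 23 per arm, assuming all 68 were randomized. The documents state no mortality, interval width or coverage for survival, so there is no figure of the plan's own to reproduce. Mortality of 1% to 15% is an assumption. Background death rates in Protocol 2.6 run from 2.8% to 14.8%, but not for this population.

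**Variance with no deaths.** Greenwood: Var = S² × Σ d/[n(n − d)], summed over death times. With every d = 0 the sum is 0. The linear and log scales then give 100%-100%. On the log-log scale, log(−log 1) is undefined. No choice of scale produces an interval.

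**Exact limit for 0/23.** The lower 95% Clopper-Pearson limit for survival is 0.025^(1/23) = 0.852. The interval is 85.2%-100%, compatible with mortality up to 14.8%. With 22 patients it is 84.6%-100%.

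**Chance of the collapse.** With mortality m, the same in every arm, and no censoring, P0 = (1 − m)^23 per arm, and 1 − (1 − P0)³ for at least one of three arms. The last two columns give the coverage of linear Greenwood limits by enumeration of all binomial outcomes. Without censoring, Greenwood equals the binomial variance. A 100%-100% interval counts as a miss.

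| Assumed mortality | No deaths, one arm | No deaths, at least one of three | Linear coverage, overall | Linear coverage, given at least 1 death |
|---|---|---|---|---|
| 1% | 79% | 99% | 21% | 100% |
| 2% | 63% | 95% | 37% | 100% |
| 5% | 31% | 67% | 69% | 99.9% |
| 10% | 9% | 24% | 91% | 99.4% |
| 15% | 2% | 7% | 86% | 89% |

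Up to 10% mortality, overall coverage is almost exactly one minus the no-death chance. Clopper-Pearson covers 97.7% to 99.6% over the same range. Simulation with 10% and 20% assumed dropout (40,000 runs each) gave the same pattern: at 5% mortality the no-death chance rose from 31% to 32% and 35%.

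**One death, and why the scale matters.** S = 22/23 = 0.9565; SE = 0.9565 × √[1/(23 × 22)] = 0.0425.

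- Linear: 0.9565 ± 1.96 × 0.0425 = 87.3% to 104.0%, or 100% if clipped.
- Log-log: 72.9% to 99.4%.
- Exact: 78.1% to 99.9%.

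The lower limit moves by 14.4 points (87.3 − 72.9) on a choice that the documents leave to the programmer.

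**Effect of the smaller trial.** Protocol 9.1 says "it is expected to randomize on average additional 174 patients" after the first 150. That makes 324, or 108 per arm. The no-death chance at 5% mortality would then have been 0.95^108 = 0.4%, against 31% now. At 1% it would have been 34%, against 79%.

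**Deaths as censored.** The general rule in SAP 4.4 censors patients who die at their date of death, with no exception for overall survival. SAP 14.1.3 computes overall survival to the date of death or censoring. Read literally, 4.4 leaves every survival curve without events however many patients die, and the collapse would then occur in all three arms.

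**The case against.** The strongest reply is that this is a descriptive interval on one secondary endpoint. No test, success rule or decision uses it, and the number of deaths, a listing of deaths and the numbers at risk will be reported anyway. That stands and limits the weight of the point.

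A reader might infer more than the documents support:

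- **That the limits also cover far below 95% whenever deaths are few.** The table does not show this. The low overall coverage up to about 10% mortality is the no-death collapse counted again. With at least one death, linear limits cover 99% or more up to 10%. They fall to about 89% at 15%, and only if the linear scale is used, which neither document states. Greenwood's variance also underlies log-log limits.
- **That the SAP explicitly puts Greenwood limits on the day 7, 14 and 28 estimates.** It names them only for the median and quartiles. The link to the landmarks comes from the general sentence in Protocol 9.5, which SAP section 18 does not change.
- **That NE would be false precision.** NE with its footnote is honest about the lack of an estimate. What is lost is the bound.
- **That no deaths is the expected result.** No mortality is given. At 15% the chance is about 2% per arm.

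A further objection is that exact binomial limits need known vital status. Protocol 6.2.4 withdraws patients from the study once oxygen criteria are met, and those may be the patients at highest risk. A fixed denominator of 23 would then overstate precision. This does not rescue Greenwood, but it puts a condition on the fix.

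**Conclusion.** The point holds for the no-event case. At about 23 per arm, the prescribed method cannot give a survival interval for an arm without deaths, whereas the exact interval is 85.2%-100%. The chance that at least one arm is affected is 99% at 1% mortality, 67% at 5% and 7% at 15%. These figures assume 23 per arm, equal mortality across arms and no censoring. The unnamed scale is a smaller, separate gap that matters once an arm has a death. The contradiction between SAP 4.4 and 14.1.3 is the more basic one, since it decides whether the survival curve contains any events. None of this touches the primary analyses. The change is worth making because it is nearly free, but the trial's conclusions do not depend on it.

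**What to change.** In SAP 4.4 and 14.1.2:

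- Report the proportion alive at days 7, 14 and 28, which Protocol 9.5.2.2 already promises, with exact Clopper-Pearson 95% limits. Use as denominator the patients whose vital status is known at that day, and state the number unknown in each arm.
- For other Kaplan-Meier landmarks, name log-log limits. Use exact binomial limits where the estimate is 0% or 100% and follow-up is complete.
- Reconcile the rule in 4.4 that censors patients at death with the derivation in 14.1.3, so that death is the event for overall survival.

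Record the change in SAP section 18, since it departs from the Greenwood sentence in Protocol 9.5. The cost is a few sentences and an exact option in the frequency procedure, with no new data. The downside is wider intervals, which show how little 68 patients can say about survival.
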